### Sample size:

The primary endpoint of the study is time to successful tracheal intubation. Sample size is based on a calculation of 10.0 s as the clinically relevant difference in intubation time, with a prospective power analysis at 80% power and 0.05 level of significance. It shows that a sample of 28 laryngoscopists would be required. This will be a cross over study, hence we will recruit 30 laryngoscopists to also account for dropouts and protocol breaches. In view that the time to successful intubations data are not normally distributed, we will use the Mann Whitney U test to analyse intubation times. Categorical data such as number of intubation attempts will be evaluated for differences among the groups using the chi-square test. All statistical analyses

will be performed using IBM SPSS statistics 23 database. A value of p < 0.05 is considered significant.

[figure not shown]

Figure 1 (Box A). Dimensions are 50 cm by 50 cm (height x width), with a thickness of 40 cm. (Source: https://sites.google.com/view/aerosolbox/design)

[figure not shown]

Figure 2 (Box B). Dimensions are 46 cm x 58 cm (height x width) with a thickness of 51cm. The upper portion of the box facing the intubator is made slanted at a 150 degree angle hence providing better ergonomics to the intubator. The curved design at one end of the box is to accommodate the obese/big build patient whose shoulder breadth may be wider than the box's width.

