### **Objectives:**

We aim to compare the relative intubating efficacies of these two boxes. This study assesses the time to successful intubation as the primary outcome. Our secondary outcomes will be the quality of the laryngoscopy view (objectively defined as "percentage of glottic opening" / POGO) and ease of intubation.

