### Methodology:

This is a prospective randomized cross over trial to compare the time for intubation using these two devices by our anaesthetists. The planned duration from planning to recruitment to completion of study will be from 1st May 2020 to 31st December 2020. We will recruit eligible anaesthetists after obtaining written informed consent. The anaesthetist should have more than 5 years of experience with intubation as well as experience with intubating patients using videolaryngoscope for more than 20 times.

The anaesthetist will be randomised to intubate the manikin in either Box A or Box B first. The primary endpoint which is the time to successful intubation (defined as the interval from insertion of the laryngoscope blade into the mouth to inflation of the tracheal tube cuff) will be recorded. Other endpoints are the numbers of intubation attempts (each attempt defined as complete removal of video laryngoscope from mouth and reinsertion) will be recorded. Failed insertion is defined as the entire intubation procedure taking more than 120 seconds or more than 3 insertion attempts.

The participants will evaluate their intubation experience using both boxes with a questionnaire based on the ISO9421-11 standard, that is effectiveness, efficiency and satisfaction.

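### The single primary time is recorded under both direct and videolaryngoscopy, no readable text says which comparison decides, and the planned Mann-Whitney test ignores the crossover pairing

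*Combined protocol and SAP*

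**What the plan says.** The Objectives section says "This study assesses the time to successful intubation as the primary outcome" and the Sample size section repeats it: "The primary endpoint of the study is time to successful tracheal intubation". Methodology gives the time as "defined as the interval from insertion of the laryngoscope blade into the mouth to inflation of the tracheal tube cuff". That wording fits any laryngoscope.

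Part 2 of the data collection sheet has two blocks, one for direct laryngoscopy and one for videolaryngoscopy. Each has a row for the time to successful intubation with a column per box. Part 3 (usability) is split the same way.

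Methodology mentions video in two places. Eligibility requires "experience with intubating patients using videolaryngoscope for more than 20 times", and an intubation attempt is "each attempt defined as complete removal of video laryngoscope from mouth and reinsertion". The randomisation sentence concerns boxes only: "The anaesthetist will be randomised to intubate the manikin in either Box A or Box B first".

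For the analysis, the Sample size section says "we will use the Mann Whitney U test to analyse intubation times", with significance at p < 0.05. It gives one clinically relevant difference (10.0 s), one sample size (28, with 30 recruited) and no SD.

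**The concern.** Each anaesthetist can yield two Box A versus Box B comparisons of the primary time, while the plan provides for one endpoint, one difference and one significance rule. Nothing readable selects, ranks or pools the two. Nor is the direct-laryngoscopy time labelled secondary: the Objectives section begins "Our secondary outcomes will be the quality of the laryngoscopy view" and adds only ease of intubation, and Methodology adds only the number of attempts.

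The claim that one box is faster could therefore rest on whichever technique gave the more favourable result, and a reader of the report could not tell whether that choice came before or after the data.

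Two related points affect the same comparison. Mann-Whitney treats the two boxes' times as independent samples although the same anaesthetist produces both. And the attempt definition, which feeds the failure rule (more than 120 seconds or more than 3 attempts), is worded for the video laryngoscope only.

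**Working it through.** **The plan's own figure.** Inputs from the Sample size section: difference 10.0 s, power 80%, level 0.05 (two-sided assumed), n = 28. No SD is stated, so 28 can only be solved backwards.

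- Paired, normal approximation: n = (SD of difference × (1.960 + 0.842) / 10)². Rounding up to 28 needs an SD of the within-person difference of about 18.6 to 18.9 s. With the paired t distribution it is 17.9 to 18.2 s.
- Unpaired, 28 per group: n = 2 × (SD × 2.802 / 10)² needs an SD of about 13.1 to 13.4 s.

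The documents contain none of these SDs, so 28 is neither confirmed nor refuted, and nothing ties it to one technique.

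**False positives if either technique's result may count.** The correlation ρ between the two test statistics is an assumption. For two valid tests, each at two-sided 0.05, the rate is 1 − P(|Z1| ≤ 1.96 and |Z2| ≤ 1.96). At ρ = 0 this is 1 − 0.95² = 9.75%.

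| ρ | 0 | 0.3 | 0.5 | 0.7 | 0.9 |
|---|---|---|---|---|---|
| At least one false positive | 9.75% | 9.5% | 9.1% | 8.35% | 7.0% |

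**The same question under the planned test.** Null simulation with n = 30, lognormal times, four times per anaesthetist and 100,000 runs per setting. Ranges in the last column cover different cross-technique correlations.

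| Assumed between-box correlation | Single Mann-Whitney | Either of two Mann-Whitney tests |
|---|---|---|
| 0 | 5.0% | 7.2 to 9.7% |
| 0.2 | 3.0% | 5.0 to 5.8% |
| 0.3 | 2.1% | 3.3 to 4.1% |
| 0.5 | 0.8% | 1.3 to 1.6% |

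A single paired Wilcoxon test stayed between 4.8% and 5.1% in all settings.

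**Power cost of ignoring the pairing.** Let r be the between-box correlation and m the expected value of the paired statistic. The unpaired statistic then has mean m√(1 − r) and standard deviation √(1 − r), so its power is about Φ(m − 1.96/√(1 − r)). If 28 gives 80% paired power, then at n = 30, m = 2.80 × √(30/28) = 2.90.

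- r = 0.3: Φ(2.90 − 2.34) = 71%.
- r = 0.5: Φ(2.90 − 2.77) = 55%.

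Simulation with normal data gives about 69% and 54%. Across the paired SDs consistent with 28, the simulated ranges are about 67 to 71% and 51 to 56%; the paired Wilcoxon test has about 79 to 82%.

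If 28 was instead calculated as an unpaired size per group, then taking n at that size, Mann-Whitney power at r = 0.5 is Φ(0.842/√0.5) = 88%, against Φ(2.802/√0.5 − 1.96) = 98% for a paired test. The loss remains, but power does not fall below 80%.

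**The case against.** The strongest reply is that video is plainly intended. It is the only technique named in eligibility, the attempt definition is written for it, and no Methodology or analysis sentence mentions direct laryngoscopy. A data form lists what is collected and does not define endpoints. This is a reasonable inference and a good reason to designate video, but it is not a designation: the time definition is generic, and the direct-laryngoscopy time has no stated status.

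A second reply is that the rule may sit in the flow chart or Appendix B, of which only the headings could be read. That stands. The point is limited to the readable text, and it would be wrong to say that the plan has no rule.

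Three stronger readings are tempting.

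- A reader might infer that two primary tests are planned, with a false-positive rate near 10%. The plan does not say so, and under the planned Mann-Whitney test there is no excess over 5% from a between-box correlation of about 0.3 upward.
- A reader might infer that Mann-Whitney breaches the 5% level. For a single comparison it does not; with positive correlation it falls below 5%, and the cost is power.
- A reader might quote how often the two techniques would disagree on significance: 32% of trials at test correlation 0 and 10% at 0.9, with 80% power assumed for each. That is an illustration under assumed inputs, not a property of this trial, and naming one primary comparison would not change it.

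**Conclusion.** The point holds as an ambiguity in the primary endpoint: one primary time, two recorded versions of it, and no readable rule for which decides. The harm is that the choice is open after the data are seen.

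Its size in false-positive terms depends on the test and on correlations that the plan does not give. It is 7.0 to 9.75% for valid paired tests if either result counts. With the planned test it is above 5% only at between-box correlations up to about 0.2. Zero correlation is the least natural case, since the same anaesthetist uses both boxes.

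The unpaired test is a separate weakness of the same comparison: about 69% or 54% power at assumed between-box correlations of 0.3 or 0.5, where a paired design was meant to have about 80%. Those two figures assume normal data and that n was set for a paired comparison, which the plan does not state. The issue should be fixed and is easily fixed. Confidence is moderate because of the unreadable flow chart and Appendix B.

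**What to change.** Before data are seen:

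1. Designate the Box A versus Box B time under one technique as the single primary comparison at 0.05. The choice is the investigators'; videolaryngoscopy fits the Methodology text. If the flow chart or Appendix B already designates one, repeat it in the Objectives and Sample size sections.
2. Label the other technique's time secondary, or test it at 0.05 only if the primary comparison is significant. With that fixed order and valid tests, the overall error rate stays at 5%.
3. Replace Mann-Whitney for intubation times with a paired test suited to the crossover, such as Wilcoxon signed-rank on within-anaesthetist differences. The reason is power and a match to the design, not an excess of false positives.
4. Reconcile the video-only attempt wording in Methodology with the direct-laryngoscopy block on the data sheet.

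The cost is three or four sentences and no added participants. The downside is that a difference seen only under the non-primary technique would not be confirmatory.

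### The plan names 10 s as the relevant difference but gives the primary endpoint only a Mann-Whitney p-value, with no estimate or interval in seconds to set against it

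*Combined protocol and SAP*

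**What the plan says.** All the statistical planning is in the Sample size section. It sets the relevant difference ("Sample size is based on a calculation of 10.0 s as the clinically relevant difference in intubation time"), then the error rates ("with a prospective power analysis at 80% power and 0.05 level of significance"), then the result ("It shows that a sample of 28 laryngoscopists would be required"). The target is raised slightly: "we will recruit 30 laryngoscopists to also account for dropouts and protocol breaches". No SD, sidedness, correlation or dropout rate is given.

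For the primary endpoint the section says "we will use the Mann Whitney U test to analyse intubation times", because the times are not expected to be normally distributed. The criterion for all tests is "A value of p < 0.05 is considered significant".

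The Methodology section describes the design: "This is a prospective randomized cross over trial to compare the time for intubation using these two devices by our anaesthetists". The data collection sheet (Part 2) records time in seconds for each box side by side, so every anaesthetist supplies a within-person difference. Neither section plans a mean, median or Hodges-Lehmann difference, a confidence interval, or a comparison of the result with 10 s.

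**The concern.** The Objectives section asks how the two boxes compare in intubating efficacy. That is a question of size as well as direction, and the plan says what size matters: 10 s. A Mann-Whitney p-value gives no number of seconds, so the primary result cannot be read against that figure.

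The gap works in both directions. A small p-value could accompany a difference below 10 s. A large p-value could come from data that still allow a 10 s difference. In neither case would the planned output tell the reader which situation applies. The investigators are also evaluating their own redesign, which the Introduction already describes as ergonomically better. A prespecified estimate and interval would keep the conclusion in proportion.

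**Working it through.** **Inputs from the Sample size section:** difference 10.0 s, power 80%, significance level 0.05, n = 28 required, n = 30 recruited. **Not given:** any SD, or whether the test is one- or two-sided.

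**1. The plan's own figure.** Without an SD the 28 cannot be reproduced, only inverted. For a paired comparison, n = ((z_α + z_power) × SD_diff / 10)², so SD_diff = 10 × √28 / (z_α + z_power).
- Two-sided, normal: 10 × 5.292 / 2.802 = 18.9 s.
- Two-sided, exact noncentral t: 18.2 s.
- One-sided, normal: 21.3 s.
- Read instead as two independent groups (two-sided t): SD of times 13.1 s for 28 per group, or 9.1 s for 14 per group.

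All of these are back-solved assumptions.

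**2. Precision of a paired difference at n = 30.** The half-width of the 95% interval is h = t(0.975, 29) × SD_diff / √30 = 2.045 × 18.2 / 5.477 = 6.8 s. Range:
- SD 0.75 times the implied value: h = 5.1 s.
- SD 1.25 times the implied value: h = 8.5 s.
- One-sided origin: 2.045 × 21.3 / 5.477 = 8.0 s.
- 14-per-group origin with uncorrelated times: SD_diff = 9.1 × √2 = 12.9 s, so h = 2.045 × 12.9 / 5.477 = 4.8 s.

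**3. What the interval would show that a p-value does not.** With h = 6.8 s and a t interval:
- Observed difference between 6.8 and 10 s: significant, but the estimate is below 10 s. Example: 8 s gives 1.2 to 14.8 s.
- Observed difference between 10 − 6.8 = 3.2 s and 6.8 s: not significant, but the interval includes 10 s. Example: 5 s gives −1.8 to 11.8 s.
- The whole interval lies above 10 s only if the observed difference exceeds 10 + 6.8 = 16.8 s.

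The first band exists whenever h is below 10 s, which holds for every variant in step 2. The second exists only if h exceeds 5 s. It is wide at h = 8.5 s (1.5 to 8.5 s), very narrow at 5.1 s (4.9 to 5.1 s) and absent at 4.8 s.

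**4. The planned test.** Steps 2 and 3 describe a paired estimate. The Mann-Whitney test ignores pairing, so it was simulated separately (30 against 30 times, normal data, 2,000 runs per setting).
- Uncorrelated times, SD about 13 s: significant in 29–31% of runs for a true 5 s difference and 51–52% for 7 s. It was significant with an estimated shift below 10 s in about 21–23% and 31% of runs.
- Correlation 0.5, SD of times 18.2 s (so SD of differences also 18.2 s): significant in 10% of runs for 5 s and 23% for 7 s. A paired t test with the same SD of differences has 31% and 53% power.

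So the planned test can be significant with an estimate below 10 s. When the two times from one anaesthetist are correlated, it can also differ considerably from a paired analysis. A paired interval printed beside a Mann-Whitney p-value could therefore contradict it.

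**The case against.** Several points against this concern are sound.

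**Powering on a relevant difference and testing against zero is standard practice.** At 80% power and two-sided 0.05, the smallest significant difference is about 1.96 / 2.80 = 0.70 of the design difference in almost any superiority trial. That ratio is not a defect of this plan. What remains is the missing estimate.

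**A reader might infer that a significant difference of a few seconds would be announced as one box being better, or that p ≥ 0.05 would be announced as no difference.** The documents contain neither rule. They give a significance level and an aim to compare the boxes. Under the implied SD, a true 5 s difference reaches significance only about 30% of the time even with a paired t test, and less often with the planned test if times are correlated. The documents support could, not would.

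**The cut-offs in seconds belong to a paired t analysis on a back-solved SD.** This stands. They indicate the precision available and are not the behaviour of the Mann-Whitney test.

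**A formal relevance rule would go too far.** This also stands. Requiring a point estimate of at least 10 s would fail about half the time when the true difference is exactly 10 s. Requiring the interval to lie within ±10 s would add an equivalence claim that the trial does not make. Neither is needed.

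**Nothing prevents the investigators from reporting an estimate anyway.** True, since times are recorded in seconds. But the choice of estimate and its pairing would then be made after the data are seen.

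**Conclusion.** The concern holds as an omission. The plan defines relevance in seconds and then plans a primary analysis that returns no seconds, so the result could not be judged against 10 s in either direction.

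If the 28 rests on a two-sided paired t calculation, a paired difference at n = 30 would carry a 95% interval of about ±6.8 s (5.1 to 8.5 s if the SD is 25% lower or higher than implied). At 6.8 s, a significant result with an estimate below 10 s and a non-significant one compatible with 10 s are both realistic. The size of either band depends on an SD that the protocol does not state.

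The documents do not show that the investigators intend to present a small difference as a meaningful advantage, and testing against zero is not an error. The trial can run as designed. What is missing is a prespecified estimate with its interval.

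**What to change.** Add to the Sample size section, in place of the sentence on the Mann-Whitney test: *The primary result will be the within-anaesthetist difference in intubation time (Box A minus Box B) in seconds, reported as the paired Hodges-Lehmann estimate with its 95% confidence interval. The p-value will come from the Wilcoxon signed-rank test. The estimate and interval will be discussed against the 10 s threshold.*

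The Hodges-Lehmann estimate suits the plan's statement that times are not normally distributed. The signed-rank test is its matching test, so interval and p-value agree.

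Two definitions should be settled in the same edit. The data collection sheet records times under both direct laryngoscopy and videolaryngoscopy, so the text should say which difference is primary. Failed insertions are defined in the Methodology section but given no value for the time analysis. Both gaps affect the Mann-Whitney test equally, so the fix does not create them.

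Cost: a few sentences and one extra output, with no additional participants or data. The downside for the investigators is small: a significant but small gain, or an imprecise null result, must be described as such.

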# MILESTONES AND DATES CHART PROJECT TITLE: TAIWAN "AEROSOL BOX" VERSUS UMMC "INTUBATION BOX": CLINICAL EVALUATION OF THE "INTUBATION BOX" FOR EASE OF INTUBATION

									YEA	R 202	0							
	Apr	Apr	Ma	May	June	June	Jul	Jul	Aug		Sept	Sept	Oct	Oct	Nov	Nov	Dec	Dec
	1-	16-	у	16-	1-15	16-	1-	16-	1-	16-	1-	16-	1-	16-	1-	16-	1-	16-30
	15	30	1- 15	31		30	15	31	15	31	15	30	15	31	15	30	15	
ACTIVITIES			13															
Submission for ethics committee approval																		
Preparation of resources required																		
Data collection																		
Data entry																		
Data analysis																		
Writing of report																		
Submission of completed paper to ISI journal																		

Part 1: User profile			
Name:			
Professional category:	:		
Anaesthesia experienc	ce:		
Age:			
Gender:			
Part 2: Intubating co	onditions pr	ofile	
For direct laryngoscop	-		
		T-: D	HMMC D
Findings Time for successful		Taiwan Box	UMMC Box
(seconds)	IIIIuoaiioii		
Number of intubatio	n attempts		
POGO grading (%)			
Cormack Lehane gra	ade (1-4)		
For videolaryngoscop	y:		
Findings		Taiwan Box	UMMC Box
Time for successful		Turwun Don	CHAIC BOX
(seconds)			
Number of intubation	n attempts		
POGO grading (%)			
Cormack Lehane gra	ide (1-4)		
Part 3: Usability pro	file		
In this section, we wo		now the usability of this eq	uipment (Taiwan Box vs UMMC Box)
during intubation.			
When using for intul	hation with	direct laryngoscopy:	
Findings	vativn With	Taiwan Box	UMMC Box
On a scale of 0-			
10, how easy was	0	10	0

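### The primary endpoint of a within-person crossover is tested with the unpaired Mann-Whitney U test, and N=28 cannot be tied to that or any other test

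*Combined protocol and SAP*

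**What the plan says.** The Methodology section sets out the design: "This is a prospective randomized cross over trial to compare the time for intubation using these two devices by our anaesthetists". What is randomised is the order: "The anaesthetist will be randomised to intubate the manikin in either Box A or Box B first". Every participant uses both boxes. The same section says "The participants will evaluate their intubation experience using both boxes with a questionnaire", and the data collection sheet has a Taiwan Box column and a UMMC Box column for each user.

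The Sample size section states "The primary endpoint of the study is time to successful tracheal intubation". It gives a relevant difference of 10.0 s, 80% power and a 0.05 significance level, and concludes "It shows that a sample of 28 laryngoscopists would be required", with 30 to be recruited. It then says "we will use the Mann Whitney U test to analyse intubation times". The only reason offered is that the times are not normally distributed.

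The section gives no SD, within-person correlation, sidedness or assumed test for the power calculation. The readable text contains no paired test and no period or sequence term.

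Part 2 of the data collection sheet has separate blocks for the two techniques, with headings that begin "For direct laryngoscop" and "For videolaryngoscop". Each block has a time for each box, so there are four times per person. The text does not say which pair is the primary comparison. The Methodology section leans towards videolaryngoscopy in its eligibility rule and its definition of an attempt, but does not settle the matter.

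**The concern.** Non-normality is a reason to use a rank test. It is not a reason to use an unpaired one. The Mann-Whitney U test on the raw times treats the Box A and Box B times as coming from two different sets of people. A fast operator tends to be fast in both boxes, and that operator-to-operator variation, which a crossover is meant to remove, stays in the error term.

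A rank-sum test can be valid in a two-period crossover if it compares each person's first-minus-second difference between the two order groups. The plan does not describe this; it applies the test to the intubation times themselves.

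The risk is that a real 10 s difference is reported as non-significant although the paired data would show it. Because the basis of N=28 is incomplete, the stated 80% power cannot be attached to the planned test.

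**Working it through.** **Inputs from the plan:** difference 10.0 s; power 80%; significance level 0.05; 28 required, 30 recruited; both boxes used by each person.

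**Inputs assumed:** two-sided testing, all SDs and all correlations ρ. The plan gives none of these.

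**1. Trying to reproduce N=28.** It cannot be computed forward without an SD. Solving backwards for the SD that gives 80% power at 10 s (two-sided 5%, noncentral t):

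| Reading of 28 | Noncentrality | SD implied |
|---|---|---|
| 28 pairs | 10·√28 / SD of differences | 18.2 s (differences) |
| Unpaired, 28 per box | 10·√(28/2) / SD | 13.1 s (each box) |
| Unpaired, 14 per box (28 in total) | 10·√(14/2) / SD | 9.1 s (each box) |

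If the calculation was one-sided, the first two become 20.7 s and 14.9 s. All of these fit the stated inputs, so 28 does not identify a test.

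**2. Type I error.** For two times with common SD σ, the variance of the difference is 2σ²(1−ρ), but an unpaired test uses 2σ². As a rough guide, the true two-sided error is 2Φ(−1.96/√(1−ρ)):
- ρ = 0.3: 1.96/0.837 = 2.34, giving 1.9%.
- ρ = 0.5: 1.96/0.707 = 2.77, giving 0.6%.
- ρ = 0.7: 1.96/0.548 = 3.58, giving 0.03%.

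Simulating the Mann-Whitney test itself (20,000 trials, 28 pairs, normal data) gives 1.9%, 0.7% and 0.1%. The signed-rank test stays between about 4.5% and 5%.

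**3. Power for 10 s, 28 pairs, by simulation.** Each cell shows Mann-Whitney v signed-rank.

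| Scenario | ρ = 0.3 | ρ = 0.5 | ρ = 0.7 |
|---|---|---|---|
| Paired reading (SD of differences 18.2 s), normal | 66% v 78% | 50% v 78% | 23% v 78% |
| Paired reading, lognormal, log-SD 0.5 | 86% v 86% | 77% v 87% | 54% v 88% |
| Paired reading, lognormal, mean 40 s | 77% v 81% | 69% v 83% | 54% v 86% |
| Unpaired, 28 per box (SD 13.1 s), normal | 81% v 89% | 85% v 96% | 90% v >99% |
| Unpaired, 14 per box (SD 9.1 s), normal | 99% v >99% | >99% v >99% | >99% v >99% |

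In the paired reading the SD of differences is held at 18.2 s, so the per-box SD is 18.2/√(2(1−ρ)): 15.4, 18.2 and 23.5 s. This is why Mann-Whitney power falls as ρ rises while signed-rank power stays level. In the last row all 28 people contribute a time in each box, twice what that calculation would have assumed.

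**4. Why order matters.** Take the paired reading with normal data, and let the first attempt be slower by 0, 5, 10 or 15 s. Signed-rank power is 78%, 75%, 67% and 54%. The rank-sum test on period differences (14 v 14) stays at about 76%.

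**The case against.** The strongest reply is that the harm is conditional. The error is conservative, so a significant Mann-Whitney result would still be credible. Power falls clearly below 80% only if 28 came from a paired calculation. With 28 per box it is 81% to 90%, and if 28 was an unpaired total of 14 per box it is about 99% or more. The largest losses come from normal data, whereas the plan expects non-normal times; the skewed scenarios are milder, and one shows no loss at a correlation of 0.3. None of the models includes the 120-second failure limit.

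All of that stands as a limit on the size of the loss. It does not rescue the test. Under every reading the p-value is miscalibrated at any positive correlation, and the number of compatible readings is itself why the 80% cannot be verified.

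Three smaller points also stand. The basis of 28 is not wholly absent, since the difference, power and significance level are given. The 14 v 14 split is an assumption, because the plan states no balanced allocation. A failed insertion has no time to success, so that person's difference is undefined until a rule is set; this gap exists under the present plan too.

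**Conclusion.** The concern holds. The only test named for the primary endpoint does not match the design, and this should be corrected before the analysis. The direction is certain for positive within-person correlation: p-values are too large, with a true type I error of about 2% to 0.1% at correlations of 0.3 to 0.7. The power cost is not certain. Against the signed-rank test it runs from negligible (14 per box, or one skewed scenario at 0.3) to a fall from about 78% to 23% (paired reading, normal data, correlation 0.7). These sizes rest on assumed SDs and correlations and on two-sided testing. The number 28 is not shown to be wrong; it cannot be checked or tied to the planned test.

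**What to change.** Replace the Mann-Whitney U test on raw times with an analysis that uses the pairing and the randomised order:

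- **Preferred:** compute each anaesthetist's first-box minus second-box time and compare these differences between the two order groups with a rank-sum test. Half the Hodges-Lehmann shift, with its 95% CI, estimates Box A minus Box B and is set against 10 s.
- **If order is not adjusted for:** use the Wilcoxon signed-rank test on Box A minus Box B.
- State before data collection which technique's pair of times is primary; the other is secondary. Say how a pair with a failed insertion enters the analysis.
- Restate the basis of 28 for the chosen test, with a sourced SD of within-person differences and the sidedness. If no source exists, give the power of 28 completers over a range:

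| SD of differences (10 s, two-sided 5%, normal) | 15 s | 17.5 s | 20 s | 25 s |
|---|---|---|---|---|
| Rank-sum on period differences (14 v 14) | 90% | 79% | 68% | 48% |
| Signed-rank | 91% | 81% | 70% | 50% |

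The cost is a few sentences and a source for the SD. Box order must be kept in the dataset. Changing the test needs no added measurements or participants, so the 30 recruits can stay. If the sourced SD is well above 17.5 s, the sponsor should acknowledge that power is below 80%. That would be a sizing question in its own right, not a cost of changing the test.
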